1.0 INTRODUCTION

Phyllodes tumors of the breast are uncommon neoplasms which present in young women (median age 45 years). Phyllodes tumors have been characterized by the World Health Organization based on histologic features as benign, borderline or malignant (1,2). Diagnostic histologic features include the number of mitoses per high power field, presence of infiltrating tumor near the margins, and cellularity and degree of stromal atypia. This categorization predicts the tumor's metastatic potential fairly well: in one review 0.4%, 4.3% and 22% of patients with benign, borderline and malignant phyllodes tumors developed metastases (3).

According to recent SEER data, approximately 500 women are diagnosed with malignant phyllodes tumors in the US each year and about half of those patients are treated with breast conserving resections as the only therapy (4). We reviewed the literature to determine the rate of local recurrence after margin-negative breast conserving resection of borderline malignant and malignant phyllodes tumors (5). A total of 13 studies were identified. Local recurrences occurred in 37/124 (21%) patients. Twelve of fifty (24%) patients with borderline malignant tumors and 25/124 (20%) patients with malignant phyllodes tumors experienced a local recurrence. The median follow-up in these studies ranged from 3.1- 9 years. Of note, the vast majority of recurrences occurred within 2 years of surgery: the median time to recurrence was 24 months or less in all but one of these studies.

This local recurrence rate is unacceptably high, as there are multiple adverse consequences of in-breast recurrences. There is substantial psychological morbidity. There is cosmetic morbidity: patients with recurrent phyllodes tumors will require wide local re-excision or mastectomy. Furthermore, several studies have shown that local recurrence of phyllodes tumors is a strong predictor of metastatic spread (6-8). A multivariate analysis in one of these studies indicated that local recurrence of phyllodes tumors was associated with a significantly increased risk of death (8). Concern remains for the potential for local recurrences to metastasize, as was demonstrated in a recent meta-analysis of randomized prospective studies of patients with invasive breast cancer (9). In this study it was determined that for every 4 local recurrences that were avoided, one breast cancer death was prevented.

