In 1998 we initiated a prospective single arm study (DMS 9801) to determine whether adjuvant radiation therapy after breast conserving resection of borderline and malignant

phyllodes tumors decreases the local recurrence rate (5). Forty six women were treated at 30 different institutions. The mean patient age was 49 years (18-76). Thirty patients (65%) had malignant phyllodes tumors, the rest were borderline malignant. The mean tumor diameter was 3.7 cm (0.8-11 cm). Eighteen patients had a negative margin on the first excision. The median size of the negative margin was 0.35 cm (range <0.1-2 cm). Twenty eight patients underwent a re-excision because of positive margins in the initial resection. Two patients died of metastatic phyllodes tumors. With a median follow-up of 56 months (range 12-129 months), none of the 46 patients developed a local recurrence (local recurrence rate zero (95% CI 0 - 8%)). We concluded that adjuvant radiation therapy decreased the local recurrence rate after breast conserving resections of phyllodes tumors.

A recent retrospective report from the Rare Cancer Network also provides strong support for the use of adjuvant radiation therapy after resection of phyllodes tumors (4). Of 159 patients with borderline or malignant phyllodes tumors, 109 were treated with breast conserving surgery and 50 underwent mastectomy. Thirty six received adjuvant radiation therapy. When all 159 patients were considered the percentage free of local recurrence at 10 years in the group that received radiation therapy was significantly better than the group that did not receive radiation therapy (86% vs 59%, p= 0.02). Of the 109 patients treated with breast conserving surgery, 11 underwent radiation therapy and 68% were free of local recurrence at 10 years compared to 54% of the 98 patients who underwent lumpectomy without radiation therapy. Of the 50 mastectomy patients, 25 underwent radiation therapy and 92% were free of local recurrence at 10 years, compared to 78% of the patients undergoing mastectomy without radiation therapy. While the trends in each of these subgroups favor radiation therapy, the differences were not statistically significant. In multivariate analysis the only favorable independent prognostic factor was the use of radiation therapy.

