6.0 POST-THERAPY EVALUATION

All patients will be encouraged to perform monthly breast self examination and will be followed with physical exams of the affected breast by their surgeon or radiation oncologist. These physical exams should occur every 6 months (+/- 3 months) after the initial resection through year 5 (ie. at 6,12,18,24,30,36,42,48,54,and 60 months) and then every 12 months (+/- 3 months) years 5 through 10 (ie. 72, 84, 96,108 and 120 months). Mammograms will be obtained at 6 months (+/- 3 months) and 12 months (+/- 3 months) and then annually for 10 years after the initial resection. A 5 year minimum follow-up should detect almost all recurrences, since the

vast majority of local recurrences occur within 2 years of initial excision. Since it is possible that radiation therapy may delay, but not prevent recurrences, we propose a 10 year follow-up. Suspicious masses discovered by physical exam or by imaging studies will be biopsied per routine clinical care. Biopsy proven phyllodes tumor recurrences should be reported promptly to the Principal Investigator. Patients will be terminated from the study at the time of death or after 10 years of follow-up, whichever comes first.

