8.1 Statistical analysis

The rate of in-breast recurrence will be calculated with an exact binomial confidence interval. A binomial test (i.e., one sample proportion test) will be used to compare this rate to the rate of 21% determined from the literature for margin negative breast conserving resection alone. To address the secondary aim the rate from this study will be compared to the rate (0/46) obtained in the study using adjuvant whole breast radiation using a Fisher's exact test.

Additional analysis will include descriptive summaries of adverse events, time to recurrence and survival. Time to recurrence and survival will be estimated separately for the borderline and malignant tumor groups using the product limit method.

Sample Size and Power Considerations

A total sample of 50 patients will be enrolled and followed for recurrence. This yields sufficient power (i.e., 80%) to detect that adjuvant partial breast radiation is better than margin negative breast conserving resection alone, if indeed this adjuvant therapy reduces the rate to 6% or less, and the rate with resection alone is 21%. This calculation sets the type I error rate (α) at the usual 0.05. The 95% exact binomial confidence interval has an expected range of 1% to 15% if the actual rate is 5% (whereas it is 0% to 8% if the actual rate is 1%, and it is 4% to 22% if the actual rate is 10%). In comparison to the adjuvant whole breast radiation in which our prior study found no in-breast recurrences in 46 women, partial breast radiation will be identified as having a significantly higher rate if its actual rate is 15% or higher (assuming an α =0.5, and use of a Fisher exact test).

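### The secondary comparison with DMS 9801 sets no common follow-up horizon, so Fisher's test on crude counts can be biased in either direction

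*Combined protocol and SAP*

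**What the plan says.** Objective 2.2 and Section 8.0 make the comparison with whole breast radiation in DMS 9801 a secondary objective. Section 8.1 carries it out with Fisher's exact test: "the rate from this study will be compared to the rate (0/46) obtained in the study using adjuvant whole breast radiation". On size it says "A total sample of 50 patients will be enrolled and followed for recurrence", without saying for how long before the comparison is made.

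The control result is described in Section 1.0: "With a median follow-up of 56 months (range 12-129 months), none of the 46 patients developed a local recurrence". In this study, Section 6.0 states: "Patients will be terminated from the study at the time of death or after 10 years of follow-up, whichever comes first". The reason given for the long surveillance is: "Since it is possible that radiation therapy may delay, but not prevent recurrences, we propose a 10 year follow-up". The same section regards five years as a minimum that would catch nearly all recurrences, because the "vast majority of local recurrences occur within 2 years of initial excision".

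The only time-to-event analysis in Section 8.1 is a product-limit estimate by tumor grade within this study, listed among additional analyses. It is not linked to the DMS 9801 comparison.

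**The concern.** A crude proportion depends on how long patients were observed. Fisher's test treats each patient as a completed yes or no, so a DMS 9801 patient seen for 12 months counts as a full non-event, on a par with one seen for 129 months. The plan does not say at what follow-up this study's proportion is taken, so the two proportions may describe different periods of risk. The protocol's own reason for a 10-year follow-up, possible delay of recurrence, is the situation in which this matters most.

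At stake is the reading of partial against whole breast radiation. A late count could make partial breast radiation look worse because its patients were watched longer. An early count could make it look equivalent because they were watched for less time.

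**Working it through.** **Inputs from the documents.** n = 50 and control 0/46 (Section 8.1); control median follow-up 56 months, range 12 to 129 (Section 1.0); follow-up to 120 months (Section 6.0); accrual of 12 per year (Section 8.2).

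**Assumptions.** Equal recurrence hazards under both treatments; a 4% risk at 56 months, which lies inside the 0 to 8% interval that Section 1.0 gives for 0/46; uniform accrual; no deaths or losses. The shape of the recurrence-time distribution is also assumed, and is varied below.

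**1. The plan's own figure.** Two-sided Fisher p-values against 0/46 are 0.057 for 5/50 and 0.027 for 6/50, so the critical count is 6. At a true rate of 15%, P(X ≥ 6), with X ~ Binomial(50, 0.15), is 78.1%. This reproduces the 15% detectable rate in Section 8.1 if about 80% power and two-sided α = 0.05 were meant; neither the power nor the sidedness is stated. The printed α of 0.5 does not fit, since 2/50 would already be significant (p = 0.496). That is a separate slip to correct.

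**2. When follow-up matches DMS 9801.** 50 patients at 12 per year take 50 months, so the median patient enters at month 25. Median follow-up is then 25 months at the end of accrual, 56 months at month 25 + 56 = 81, and 95 months at month 120. All patients reach 120 months at month 50 + 120 = 170.

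**3. Late count: chance of a false finding that partial breast radiation is worse.**
- Constant hazard: 10-year risk = 1 − (1 − 0.04)^(120/56) = 8.4%.
- Front-loaded recurrence: among those who recur, F(t) = 1 − 2^(−t/m) with median m, and 10-year risk = 4% × F(120)/F(56). For m = 24 this is 4% × 0.969/0.802 = 4.8%. For m = 12 it is 4% × 0.999/0.961 = 4.2%.

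| Horizon and timing | Risk in this study | P(X ≥ 6), 0/46 fixed | Control count random |
|---|---|---|---|
| 56 months, matched | 4.0% | 1.4% | 0.2% |
| 120 months, m = 12 | 4.2% | 1.7% | 0.3% |
| 120 months, m = 24 | 4.8% | 3.3% | 0.6% |
| 120 months, constant hazard | 8.4% | 24% | 5.5% |

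The last column sums the probability of a significant Fisher result in the direction of worse over all control counts, with the control risk at 4%.

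For other assumed 56-month risks under a constant hazard with 0/46 fixed, 3% gives 0.4% rising to 9.4%, and 5% gives 3.8% rising to 42.2%. With m = 24, the 5% case rises only to 8.0%.

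**4. Early count.** Suppose partial breast radiation truly carried a 15% risk at 56 months, and simplify by giving every patient 25 months of follow-up. Under a constant hazard the observable risk is 1 − 0.85^(25/56) = 7.0%, and P(X ≥ 6) falls from 78% to 13%. With m = 24 the risk is 15% × 0.514/0.802 = 9.6%, and the probability is about 35%. A real excess would usually be missed.

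**The case against.** A reader might infer that the plan compares 10-year counts with 56-month counts, so that the test is biased against partial breast radiation and a significant result could come from follow-up length alone. The documents do not support this. No analysis date is given, and ten years is the end of surveillance, not a stated time for this test. Setting 10 years against 56 months also sets one study's maximum against the other's median; the longest DMS 9801 follow-up, 129 months, exceeds 120.

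The size is also open to challenge. The 24% needs a constant hazard, under which more than half of the 10-year recurrences (4.4 of 8.4 points) fall after month 56. The literature review in Section 1.0 points the other way: "the median time to recurrence was 24 months or less in all but one of these studies". The 24% also conditions on a control result that has probability 0.96^46 = 15% under the same 4% assumption, so part of it reflects a fortunate control count. Conditioning is legitimate because 0/46 has been observed, but the random-control figures belong beside it.

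Finally, the comparison is non-randomised and secondary, and Section 8.1 already discloses that it detects only rates of about 15% or more.

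These points remove a fixed direction and limit the size. They do not remove the fault. The early-recurrence evidence comes from resection series without radiation, and Section 6.0 itself allows that radiation may shift recurrences later. The product-limit analysis by grade does not put the two studies on one time scale.

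**Conclusion.** The concern holds as an unspecified and unmatched horizon, with bias possible in either direction: against partial breast radiation if counts are taken near 10 years, and in its favour if they are taken before about study month 81.

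For a late count with a fixed 0/46 and a 4% risk at 56 months, the inflation of a false adverse finding is slight if recurrences are early (1.4% to between 1.7% and 3.3%) and substantial only under a constant hazard (24%, or 5.5% with a random control count). All these figures assume equal hazards and all 50 patients observed to 120 months, so deaths and losses would reduce the effect. The documents do not settle which timing applies after radiation. The primary objective and its test against 21% do not depend on this comparison. The change is worth making because it is cheap and the secondary conclusion could otherwise mislead.

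**What to change.** - Prespecify one horizon that both cohorts support (for example 5 years) and a data cut-off. Truncate both cohorts at that horizon, using patient-level DMS 9801 follow-up dates.
- Make the main comparison an exact conditional test and confidence interval on events per person-year within the horizon. It accounts for shorter follow-up and stays valid with zero control events. The usual Kaplan-Meier difference with a Greenwood variance would give the control arm no uncertainty, and a log-rank test rests on a weak approximation with so few events. Little sensitivity is lost: with equal person-time per patient and no control events, six events in this study give (50/96)^6 = 0.020 one-sided and five give 0.038, so at two-sided 0.05 the threshold is again six.
- Keep Fisher's test as a sensitivity analysis among patients evaluable at the horizon. Define evaluability by enrolment date, not outcome, and list deaths and losses before the horizon. This matters because person-year rates can still differ between cohorts if the hazard is front-loaded and follow-up within the horizon is unequal.
- Report cumulative recurrence curves for both cohorts, and later recurrences, descriptively.
- State that a non-significant result does not show equal efficacy.

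The cost is SAP wording plus retrieval of the DMS 9801 dates. Their availability is an assumption, though the protocol describes DMS 9801 as the team's own study. No visit, patient or treatment changes. The downside is that recurrences after the horizon do not enter the formal comparison.

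### Time to recurrence by the product limit method, with deaths naturally read as censored, slightly overstates the proportion who recur; cumulative incidence would be the better descriptive estimate

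*Combined protocol and SAP*

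**What the plan says.** Section 8.1 of the combined protocol and SAP sets the primary estimate as a crude proportion: "The rate of in-breast recurrence will be calculated with an exact binomial confidence interval". The test against 21% and the comparison with DMS 9801 also use proportions (one-sample binomial and Fisher's exact).

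The time-based analyses come after these and are supplementary: "Additional analysis will include descriptive summaries of adverse events, time to recurrence and survival". The method is then named: "Time to recurrence and survival will be estimated separately for the borderline and malignant tumor groups using the product limit method".

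Three other places bear on the point:

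- Section 6.0 ends a woman's follow-up at death or at 10 years, whichever is earlier. Neither 6.0 nor 8.1 says how a death before recurrence enters the recurrence curve.
- The Introduction (1.0) gives background metastasis rates by grade: "in one review 0.4%, 4.3% and 22% of patients with benign, borderline and malignant phyllodes tumors developed metastases".
- The Introduction's account of DMS 9801 reports no local recurrence among 46 women, with a median follow-up of 56 months, and also says "Two patients died of metastatic phyllodes tumors".

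**The concern.** For survival, death is the event and the product limit method is the right tool. For time to recurrence, a woman who dies without recurring can no longer recur. Censoring her at death treats her as if she still could, with the same later risk as the women who remain. One minus the curve then estimates recurrence in a hypothetical setting without death, and it cannot fall below the proportion who actually recur.

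Such deaths do occur here. DMS 9801 had two deaths from metastatic disease and no local recurrences, so both were deaths without local recurrence.

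Two things are at stake, both matters of description:

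- The curves are shown separately for two grades that may differ in mortality, so the overstatement may differ between them.
- The primary proportion counts a recurrence-free death as no recurrence. With complete follow-up, cumulative incidence reproduces that proportion. The product limit estimate generally does not, and a reader would see two figures with no explanation of the gap.

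**Working it through.** The plan states no figure for the time-to-recurrence curves, so there is none to reproduce. The check is how far one minus product limit (R) lies above the true cumulative incidence (C) when a fraction D would die without recurrence by the horizon.

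**Inputs**

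- C = 5% and 6%: the clinically meaningful rate in 8.0 and the rate used for power in 8.1.
- D = 4.3%: 2/46 = 4.3% in DMS 9801; the borderline metastasis rate in the Introduction is the same to one decimal.
- D = 22%: the malignant metastasis rate in the Introduction, used as an upper assumption. It requires every metastasis to be fatal within the horizon and none to follow a local recurrence.
- Timing: constant recurrence hazard, or front-loaded recurrence with a 2-year half-life, because the Introduction says most recurrences come within 2 years. Horizons are 5 and 10 years. Death has a constant hazard and is independent of recurrence (assumptions).

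**Constant hazards**

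With a = −ln(1 − R) and b = −ln(1 − D),

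C = a/(a + b) × [1 − (1 − R)(1 − D)].

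This depends on the totals R and D, not on the horizon.

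- D = 22%, R = 5.64%: a = 0.0581, b = 0.2485; C = 0.0581/0.3065 × (1 − 0.9436 × 0.78) = 0.1894 × 0.2640 = 5.0%. Overstatement 0.64 point.
- D = 22%, R = 6.77%: a = 0.0701; C = 0.0701/0.3186 × (1 − 0.9323 × 0.78) = 0.2201 × 0.2728 = 6.0%. Overstatement 0.77 point.
- D = 4.3%, R = 5.11%: a = 0.0525, b = 0.0440; C = 0.5441 × (1 − 0.9489 × 0.957) = 0.5441 × 0.0919 = 5.0%. Overstatement 0.11 point.
- D = 4.3%, R = 6.13%: C = 6.0%. Overstatement 0.13 point.

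**Front-loaded recurrence**

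C is the integral of the probability of still being alive times the recurrence density, solved numerically for R.

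| True C | D | R, constant hazard | R, front-loaded, 5 y | R, front-loaded, 10 y |
|---|---|---|---|---|
| 5% | 4.3% | 5.11% | 5.08% | 5.06% |
| 6% | 4.3% | 6.13% | 6.10% | 6.07% |
| 5% | 22% | 5.64% | 5.46% | 5.32% |
| 6% | 22% | 6.77% | 6.55% | 6.38% |

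The overstatement is therefore about 0.1 point at D = 4.3% and 0.3–0.8 point at D = 22%.

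**Between these values**

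The 2/46 was seen over a median of 56 months. Carried to 120 months at constant hazard (an assumption), D = 1 − (44/46)^(120/56) = 9.1%. If both deaths were among the 30 malignant cases (grade not stated), D = 1 − (28/30)^(120/56) = 13.7%. At C = 5% with constant hazards, R is 5.24% and 5.38%, an overstatement of 0.2 and 0.4 point.

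**Extreme bound**

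If every death came before every recurrence, R = C/(1 − D). At D = 22%: 5/0.78 = 6.4% and 6/0.78 = 7.7%. Since recurrences come early, this ordering is the opposite of what the documents describe.

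**Against sampling error**

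In DMS 9801, "Thirty patients (65%) had malignant phyllodes tumors, the rest were borderline malignant". If that share carries over (an assumption), about 32 of 50 women are malignant cases. Two recurrences in 32 is 6.25%, with an exact 95% interval of 0.8% to 20.8%, and one recurrence more or less moves the estimate by 1/32 = 3.1 points.

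**The case against.** The strongest case against the point is that it changes nothing that matters. The curves are supplementary and descriptive, no test between grades is planned, and the primary and secondary analyses use proportions. A death-censored curve is also a recognised cause-specific description of local control, and 8.1 does not claim that it estimates the proportion who actually recur. All of this stands, and it is why the point is minor.

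A reader might also draw stronger conclusions that the documents do not support:

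- *That the protocol expects 22% of malignant cases to metastasize or die.* It does not. The figure is background from one review, and no section states an expected metastasis or death rate for this trial. A woman alive with metastases can still have a local recurrence. The Introduction also links local recurrence to later spread, so some metastatic deaths would follow a recurrence and would not compete with it. DMS 9801 limits that last argument, since its two deaths came with no local recurrence, but it also shows that such deaths were few.
- *That the plan says deaths are censored.* This is inferred from the method and from follow-up ending at death. It is not written.
- *That the curves will contradict the primary result.* The primary rate is for the whole sample and the curves are by grade. With incomplete follow-up the two would differ whatever is done with deaths.
- *That a visible false difference between grades would appear.* At 5% recurrence with constant hazards, the difference in overstatement is 0.64 − 0.11 = about 0.5 point, too small to see in groups of this size.

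None of this favours the named estimator over cumulative incidence for describing how many women recur. Small numbers make the estimate imprecise; they are not a reason to keep a known one-directional error that costs nothing to remove.

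**Conclusion.** The point holds as a minor improvement. On the natural reading of 8.1 with 6.0, one minus the recurrence curve overstates the proportion who recur, probably more so in the malignant group. At the plan's own rates the amount is below 1 percentage point, even when the cited 22% metastasis rate is taken as deaths without recurrence. At the death proportion seen in DMS 9801 it is about a tenth of a point. These sizes rest on independence of death and recurrence, on the assumed timing, and on censoring of deaths, which is inferred. The sample size, the binomial test against 21% and the Fisher comparison with 0/46 are untouched.

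**What to change.** In 8.1, replace the single sentence on the product limit method with a statement of two estimators:

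- Time to recurrence: cumulative incidence (Aalen-Johansen), with death without recurrence as a competing event, by grade and for all patients together. The overall estimate can then be set beside the primary proportion, which it equals when follow-up is complete.
- Survival: product limit, as now.

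The product limit recurrence curve may be kept as a secondary display for comparison with published actuarial rates. It should be labelled as cause-specific, with deaths censored, so that the death rule is written down.

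The cost is a sentence or two of text. The data are the same, the software is standard, and sample size and trial conduct do not change.

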8.0 STATISTICAL CONSIDERATIONS

The primary objective of this study is to evaluate the in-breast recurrence rate of borderline and malignant phyllodes tumors treated with breast conserving resection and adjuvant partial breast radiation therapy. Based on our literature review, the in-breast recurrence rate after margin negative breast conserving resection alone is approximately 21 percent. A clinically meaningful improvement for the experimental therapy would be an in-breast recurrence rate of 5 percent or less.

The secondary objective is to compare the local recurrence rate observed after partial breast radiation therapy with that observed in historical controls treated with whole breast radiation therapy after breast conserving resection with negative margins (study DMS 9801, ref 5). This recurrence rate was zero (0/46 patients).

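### Section 8.1 prints α = 0.5 for the Fisher comparison with 0/46, almost certainly meant as 0.05, and promises detection of a 15% rate without giving power or sidedness

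*Combined protocol and SAP*

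**What the plan says.** Objective 2.2 and section 8.0 make the comparison with study DMS 9801 (whole breast radiation, no recurrences in 46 patients) the secondary objective. The analysis text of section 8.1 sets the new rate against the one "obtained in the study using adjuvant whole breast radiation using a Fisher's exact test". It names no significance level and does not say whether the test is one- or two-sided.

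The sample size paragraph of section 8.1 treats two comparisons.

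- Primary, against 21% for resection alone: "This yields sufficient power (i.e., 80%) to detect that adjuvant partial breast radiation is better than margin negative breast conserving resection alone", if the true rate is 6% or less. On the error rate it says: "This calculation sets the type I error rate (α) at the usual 0.05".
- Secondary, against 0/46: the trial is to find "a significantly higher rate if its actual rate is 15% or higher (assuming an α =0.5, and use of a Fisher exact test". The verb is unconditional: "partial breast radiation will be identified as having a significantly higher rate". No power is given.

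The 0.5 is the only α written anywhere for the secondary comparison.

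**The concern.** A 0.5 significance level is not a credible choice for this test, and it sits in the same paragraph as a conventional 0.05. If it is a misprint, the 15% should be recoverable from 0.05 and should not be recoverable from 0.5, which can be checked.

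Taken literally, 0.5 would call 2/50 (4%) significantly worse than whole breast radiation, although section 8.0 regards a rate of 5% or less as a clinically meaningful improvement over resection alone.

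Correcting the digit leaves a second problem. The sentence speaks of detection as certain, whereas a test with 50 patients has only some probability of detecting a given true rate. Without power or sidedness, a reader cannot tell how often a 15% rate would be missed, and a result near the cutoff could be read either way.

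**Working it through.** **Inputs.** New study n = 50, detectable rate 15%, printed α = 0.5 and primary α = 0.05 (all section 8.1); control 0/46 (section 8.0). The control is held at its observed 0/46, as the plan's sentence does.

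**Step 1: p-values.** With x recurrences in 50 and none in 46, the one-sided Fisher p is C(50,x)/C(96,x). The two-sided p adds the opposite extreme table, C(46,x)/C(96,x). For x = 5, one-sided p = (50·49·48·47·46)/(96·95·94·93·92) = 0.0347, the opposite tail is 0.0224, and two-sided p = 0.0571.

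| x of 50 | one-sided p | two-sided p |
|---|---|---|
| 1 | 0.521 | 1.000 |
| 2 | 0.269 | 0.496 |
| 3 | 0.137 | 0.243 |
| 4 | 0.069 | 0.118 |
| 5 | 0.035 | 0.057 |
| 6 | 0.017 | 0.027 |

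The smallest significant count is therefore 2 at α = 0.5 (one- or two-sided), 5 at one-sided 0.05 and 6 at two-sided 0.05.

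**Step 2: power.** For cutoff c and true rate p, power = P(X ≥ c) with X ~ Binomial(50, p). At the printed α and p = 15%: 1 − 0.85^50 − 50 × 0.15 × 0.85^49 = 0.997.

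| Setting | Cutoff | Power at 10% | at 15% | at 20% | True rate for 80% power | for 90% power |
|---|---|---|---|---|---|---|
| α = 0.5, either | 2 | 96.6% | 99.7% | 99.98% | 5.9% | 7.6% |
| α = 0.05, one-sided | 5 | 56.9% | 88.8% | 98.2% | 13.1% | 15.4% |
| α = 0.05, two-sided | 6 | 38.4% | 78.1% | 95.2% | 15.4% | 17.8% |

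**Step 3: can the plan's 15% be reproduced?** Not from 0.5: even 99% power is reached at 12.6%, so 15% is not the detection limit at that level. From two-sided 0.05 it can, if 80% power is assumed: exact power at 15% is 78.1%, and a normal approximation gives 80.0%.

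**Step 4: could the 15% be an observed rate?** No. The observed cutoffs are 2/50 = 4% at 0.5, 5/50 = 10% at one-sided 0.05 and 6/50 = 12% at two-sided 0.05. The same paragraph also uses the term for the true rate in its confidence interval examples.

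**Step 5: does the 15% settle sidedness?** Not alone. At 0.05, two-sided with 80% power and one-sided with 90% power both give 15.4%.

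**Step 6: does the primary calculation help?** For n = 50 against 21%, a two-sided exact test rejects at 4 or fewer (lower tail 0.0123), with power 82.1% at 6%. A one-sided test rejects at 5 or fewer (0.0337), with power 92.2%. The stated 80% is closer to the two-sided test.

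**The case against.** The strongest reply is that this is an obvious slip that corrects itself. The usual 0.05 stands a few lines above, the confidence intervals between are at 95%, and the sentence that specifies the analysis does not contain 0.5. The paragraph's only power figure is 80%. Combined with two-sided 0.05, it gives 15.4%, so the intended meaning can be recovered. The one-sided alternative needs a 90% power that appears nowhere in the plan; at 80% a one-sided test would have given 13.1%. Finally, the sentence is not false at the printed 0.5, where power at 15% is 99.7%. The overstatement appears only after α is corrected.

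Much of this stands. It supports the misprint reading, keeps the point minor and makes two-sided the likelier intent. It does not remove the point. The 80% is tied by its wording to the primary comparison, so applying it here is the reader's inference. The word for a higher rate gives a direction but does not say how many tails are tested. And the sentence fails on either reading of α: at 0.5 the 15% is far from the limit, and at 0.05 detection at 15% is not assured.

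**Conclusion.** The point holds and is minor. The printed α = 0.5 is inconsistent with the 15% in the same sentence and is very probably 0.05. With that correction, a true 15% rate would be missed about one time in five two-sided (1 − 0.781 = 0.219) or one in nine one-sided (1 − 0.888 = 0.112). A true 10% rate would be detected only 38% or 57% of the time. At 0.05, the unstated sidedness changes the conclusion at one result, 5/50.

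These figures assume that all 50 patients are analysed, that recurrence is a simple yes/no outcome, and that the control is fixed at 0/46. That 15% was meant as a minimum detectable rate, and that the test was meant to be two-sided, are inferences; the plan states neither. The sample size of 50 and the primary comparison with 21% are unaffected.

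**What to change.** In the sample size paragraph of section 8.1, change 0.5 to 0.05, state the sidedness before the data are seen, and replace the promise of detection with the cutoff and the power. State the same α and sidedness where the Fisher test is specified.

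Suggested wording, for the likelier two-sided intent:

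> At two-sided α = 0.05, six or more recurrences in 50 are needed against 0/46; power is about 78% if the true rate is 15% and 38% if it is 10%.

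If a one-sided test was meant:

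> At one-sided α = 0.05, five or more recurrences in 50 are needed against 0/46; power is about 89% if the true rate is 15% and 57% if it is 10%.

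The cost is one digit, one rewritten sentence and a short addition to the test specification. The detection statement becomes slightly less favourable; nothing else in the design changes.
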